## 8.4.1. Time Period and Frequency for Collecting AE and SAE Information

All AEs and SAEs will be collected from the Baseline visit until the EOT visit, at the time points specified in the SoA (Section 1.3). Medical occurrences that begin before Baseline deep phenotyping but after obtaining informed consent will be recorded as Medical History, not as AEs.

All SAEs will be recorded and reported to the sponsor or designee immediately and under no circumstance should this exceed 24 hours, as indicated in Appendix 2, Section 10.2.3. The investigator will submit any updated SAE data to the sponsor within 24 hours of it being available.

Investigators are not obligated to actively seek information on AEs or SAEs after the conclusion of the study participation. However, if the investigator learns of any SAE, including a death, at any time after a participant has been discharged from the study, and he/she considers the event to be reasonably related to the study intervention or study participation, the investigator must promptly notify the sponsor.

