| 

Sleep Disturbance (8b)

CPAQ-8

Catastrophizing

    |             | X                        |                 |                |                                |                |                          |                                | X                              | Х                              |
| PI-NRS daily diaryi  |             | X                        | X               | X              | X                              | X              | X                        | X                              | X                              |                                |
| Adverse event reporting j   |             | $X^k$                    | X               | X              | X                              | X              | X                        | X                              | X                              |                                |
| 

Quantitative sensory test

fMRI

                           |             | X                        |                 |                |                                |                |                          |                                | X                              |                                |
| Wrist actigraphy l  |             | X                        | X               |                |                                |                |                          | X                              | X                              |                                |
| PROMIS-29+2  |             | X                        |                 | X              |                                | X              |                          |                                | X                              | X                              |
| Self-enmeshment task   |             | X                        |                 | X m |                                | X m |                          |                                | X                              |                                |
| Self-Complexity task   |             | X                        |                 |                |                                |                |                          |                                | X                              |                                |

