# 3. Objectives and Endpoints

**Table 3: Study Objectives and Endpoints** 

| Objectives   | Endpoints   |
|--|---|
| Primary  |   |
| To assess the safety of TRP-8802 under the conditions of this trial  | Safety during dosing sessions: vital signs (HR, BP) (Section 8.1.1); AEs (Section 8.1.2),   |
|  | Safety during trial: AEs  |
| Secondary  |   |
| To evaluate the clinical benefit of oral TRP-8802 in concert with psychotherapy to treat chronic pain symptoms in patients with FM |   |
| To assess other potential therapeutic effects of TRP-8802 assisted therapy on FM symptoms  | Participant self-reported outcomes:  • pain interference (Section 8.2.1.2)  • sleep (Section 8.2.1.3)  • chronic pain acceptance (Section 8.2.1.4)  • Patient Global Impression of Change (PGI-C) (Section 8.2.1.5) |

| Objectives  | Endpoints  |
|-------------|--|
| Exploratory |  |
| •           | Patient reported outcomes relevant to chronic pain (Sections 8.2.2.1, 8.2.2.2)  • FM survey score, affect, catastrophizing, fatigue, anxiety, depression, cognitive impairment  Dosing-specific patient reported outcomes (Section 8.2.2.3)  • Mystical experiences  • Challenging experiences  • Psychological insight  Dosing-specific therapist reported outcomes  • Monitor rating scale (Section 8.2.2.3)  Qualitative written assessment (Section 8.2.2.4) to determine subjective participant experiences  Self-pain enmeshment (Section 8.2.2.5)  Self-complexity task (Section 8.2.2.6)  QST (Section 8.2.3.1)  • Change in cuff P40 pre- and post-intervention |
|             | 
 
Visual hypersensitivity
 
fMRI (Section 8.2.3.2)
 
Change in insula-default mode network connectivity
 
Change in Glx and/or GABA in anterior insula
 
Change in evoked pressure pain (tonic cuff)
 
Change in grey matter volume
 
Wrist actigraphy (Section 8.2.3.3)
 
Sleep onset latency
 
Wake after sleep onset
 
Total sleep time
 
Sleep efficiency (%)
 
  |

AEs=adverse events; BP=blood pressure; FM=fibromyalgia; GABA=gamma aminobutyric acid; Glx=glutamine+glutamate; HR=heart rate; P40=pain rating of 40 out of 100; PD=pharmacodynamic; QST=Quantitative Sensory Testing.

Note: The aggregate weekly pain score is over a 7-day period.

CONFIDENTIAL 23 27 February, 2024

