#### 8.1.2. Adverse events

Adverse events will be assessed throughout the study as detailed in Section 8.4.

New onset of suicidal ideation will be considered an AE. Suicidal ideation will be assessed during every in-person visit using the C-SSRS and clinical assessment during participant interviews. The C-SSRS was developed by researchers at Columbia University and is widely used in clinical and research settings (https://cssrs.columbia.edu/). Significant suicidal ideation is endorsed on items 4 or 5 on the C-SSRS.

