# 8.5. Clinical Safety and Monitoring

At enrollment, potential participants will be appropriately screened for exclusionary psychiatric conditions, medical co-morbidities, and concomitant medications. In addition medical screening will include blood tests including complete blood count (CBC), comprehensive metabolic panel (CMP), urine drug screen (UDS). Subjects with any clinically significant lab abnormalities will be excluded from participation.

Throughout the entire study, suicidal ideation will be assessed during every in-person visit using the C-SSRS and clinical assessment during participant interviews. Significant suicidal ideation is endorsed on items 4 or 5 on the C-SSRS. If the patient screens positive on the C-SSRS at any time during the study, they will undergo a more detailed suicidal risk assessment by study clinician. If they are determined to be at risk of suicide they will be transferred to ED for further Psychiatric evaluation.

During administration, heart rate and BP will be assessed before TRP-8802 capsule administration and at 30, 60, 90, 120, 180, 240, 300, and 360 minutes after capsule administration. Blood pressure and pulse measurements should be preceded by at least 5 minutes of rest for the participant in a quiet setting without distractions (e.g., television, cell phones). If a patient's blood pressure is >200 systolic or >110 diastolic for more than 15 minutes (i.e. 4 consecutive readings) they will be transferred to ED whether or not they are symptomatic.

AEs will be monitored at every study visit. Study staff will also be available throughout the course of the study for emergent AEs. Throughout the administration period, therapists will assess the presence and intensity of participant behaviors, symptoms, and non-verbal cues, which includes questions about the presence/intensity of behaviors, signs, and reported symptoms, such as peacefulness, yawning, nausea/vomiting, quantity of speech, anxiety, sleepiness, crying, restlessness, visual changes, euphoria, and feelings of unreality. They will also complete assessments of mood and safety at the end of the administration sessions.

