# 9.4.2. Primary Endpoints (Safety)

The safety of treatment with TRP-8802, which is evaluated by vital signs (HR and BP) and AEs, is the primary endpoint. Vital signs and AEs will be collected from the Baseline (deep

CONFIDENTIAL 56 27 February, 2024

phenotyping) visit until the EOT visit (Day 64) at the time points specified in the SoA (Section 1.3).

Descriptive statistics will be used to present the count and the percentage of participants in the Safety Population who experience an AE.

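### AE collection and the primary AE table stop at EOT (Day 64) while C-SSRS screening runs to Visit 15 (Day 204), so new suicidal ideation found at follow-up would go uncounted

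*Combined protocol and SAP*

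**What the plan says.** Three places set the same end date. Section 8.4.1: "All AEs and SAEs will be collected from the Baseline visit until the EOT visit". Section 9.4.2, on the primary endpoint, has vital signs and AEs collected from the Baseline "visit until the EOT visit (Day 64) at the time points specified in the SoA", then reports the count and percentage of the Safety Population with an AE. In the Schedule of Activities (Table 2), the row "Adverse event reporting" is marked from Baseline to EOT and blank for Visits 14 and 15. Its footnote limits AE and SAE recording to the marked times.

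Other text runs longer:

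- Table 3 names the primary endpoint "Safety during trial: AEs".
- Section 4.4 ends participation after Visit 15.
- Table 2 marks the C-SSRS in every column, including follow-up.
- Section 8.1.2: "New onset of suicidal ideation will be considered an AE".
- Section 8.5: "AEs will be monitored at every study visit". Its suicide-risk pathway begins "If the patient screens positive on the C-SSRS at any time during the study" and continues "If they are determined to be at risk of suicide they will be transferred to ED for further Psychiatric evaluation".

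**The concern.** The trial schedules a suicidality screen at two visits after it has closed the record meant to hold a positive result. Safety is the primary objective, and the endpoint's name implies coverage of the whole trial. A reader of the final report would reasonably take the AE percentage to include everything the scheduled safety screens found. As written it would not.

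There is also a consequence for oversight. The 5.5 pause rules are defined on related SAEs and on graded, related AEs. Ideation that is never entered as an AE is never graded or judged for relatedness, so it cannot be tested against those rules. Finally, site staff at Visit 14 face conflicting instructions: 8.5 has AEs monitored at each visit, while 8.4.1 and Table 2 have collection already closed.

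**Working it through.** **Calendar.** The inputs are Dose 2 on Day 36 (4.1.4), EOT about 28 days after the last dose (4.1.6), and follow-up at 84 and 168 days after the final dose (4.1.7). The plan's own dates reproduce exactly: 36 + 28 = 64, 36 + 84 = 120, 36 + 168 = 204.

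- Dose 2 to EOT, inside the AE window: 64 − 36 = 28 days.
- Dose 2 to Visit 15: 204 − 36 = 168 days.
- EOT to Visit 15, outside the window: 204 − 64 = 140 days, or 140/168 = 83.3% of the time after the final dose.
- With the visit windows (EOT ±3, Visit 15 ±7) the uncovered stretch runs from 197 − 67 = 130 to 211 − 61 = 150 days.
- Scheduled C-SSRS assessments in that stretch: 2 (Visits 14 and 15).

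These are shares of calendar time, not of risk. The documents give no event rate and none is assumed here.

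**Effect on the primary figure.** Assume a Safety Population of 10, the planned number of completers (9.2). One participant is then 1/10 = 10 percentage points. The overall AE percentage changes by that amount only if the participant had no AE recorded before EOT. Otherwise the overall figure is unchanged and only the ideation itself is missing.

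**Non-serious new ideation found at Visit 14 or 15.** Section 8.1.2 classes it as an AE, but the same section sends AE assessment to 8.4, where 8.4.1 closes the window at EOT. Table 2 has no AE mark at that visit. Section 9.4.2 takes its AEs from the period to Day 64. The sentence in 8.5 points the other way but does not change the window, the schedule or the table. Following the three places that agree, the event is neither recorded nor counted.

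**SAEs, including HPPD, between EOT and Visit 15.**

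- Toward stopping: the 8.4.1 window and the blank Table 2 cell. The duty in 8.4.1 to notify the sponsor of related SAEs learned of later starts only after discharge from the study, so it does not reach this period for someone still attending.
- Toward continuing: 8.4.1 requires every SAE to be recorded and reported, with no end date. It lifts the duty to seek events only once participation has ended. Section 8.4 gives the investigator an undated duty to detect and record. Section 2.3 tells participants to report HPPD symptoms at once during the study period, 10.2.2 makes HPPD an SAE, and 10.1.5 sends it to the SRC.

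The two sets conflict, and nothing states which governs. Whichever does, 9.4.2 still draws its AE table from the window ending on Day 64.

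**The case against.** The best defence is that a window closing about four weeks after the last dose is a deliberate and reasonable choice. Section 4.3 gives psilocin a half-life of 3 hours, the study is uncontrolled, and attributing an event months later is weak. Sections 8.4.1 and 9.4.2 agree with each other, and C-SSRS responses at follow-up are still collected. All of that stands. It supports reporting late events separately. It does not support leaving an event that the protocol defines as an AE, found by a screen that the protocol schedules, outside the AE record without saying so.

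A reader might go further and infer that late SAEs and HPPD have no route into the record at all. The documents do not support that: the undated recording duties in 8.4 and 8.4.1 and the reporting instruction in 2.3 point to continued capture. A reader might also infer that participants go unprotected after Day 64. They do not. The clinician assessment and ED transfer in 8.5 apply throughout, and the SRC's remit covers signal detection at any time in the study.

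Nor do the documents show that late events would change dosing decisions for others. Section 5.5 has no end date, but the overlap between one participant's follow-up and another's dosing depends on an accrual pattern that is not given.

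One uncertainty remains. Sections 8.1.2 and 8.5 tie suicidality assessment to in-person visits, and 4.1.7 describes Visits 14 and 15 only as patient-reported outcomes. Table 2 nevertheless marks the C-SSRS there.

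**Conclusion.** The point holds for new-onset suicidal ideation. Under 8.4.1, Table 2 and 9.4.2 as written, ideation first found at Visit 14 or 15 is left out of the AE record and the primary AE percentage, and is not graded or assessed against 5.5. For SAEs, including HPPD, the finding is narrower: the wording is contradictory and should be reconciled.

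The size is 140 of the 168 days after Dose 2 and two scheduled C-SSRS assessments. The number of events affected is unknown and may be zero. The conclusion assumes that the C-SSRS is given at follow-up as Table 2 marks it, and that staff follow the explicit window rather than the general sentence in 8.5. Because text points both ways, confidence is medium. This is a cheap improvement to recording and tabulation; it does not allege a lapse in immediate participant safety.

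**What to change.** Amend 8.4.1, 9.4.2 and the AE row of Table 2 as follows.

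1. From EOT through Visit 15, record all SAEs (including HPPD) and new-onset suicidal ideation (including C-SSRS item 4 or 5). Grade each one, assess relatedness, send it to the SRC and apply the existing 5.5 triggers.
2. Where an ED transfer under 8.5 occurs, record the underlying condition as the AE or SAE, not the transfer. This matches Appendix 2, which records the diagnosis or condition rather than the procedure it leads to.
3. In 9.4.2, tabulate EOT-to-Visit 15 events separately from Baseline-to-EOT AEs, because collection after EOT would be targeted rather than complete.
4. Align the sentence on AE monitoring in 8.5 with this scope.

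No trigger or clinical threshold changes. The cost is an amendment to three sections and one schedule row, and a little more AE recording at two existing visits. The safety count may look less favourable, and some late events will need assessment although their attribution is weak.

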## 8.4.2. Method of Detecting AEs and SAEs

The method of recording, evaluating, and assessing causality of AEs and SAEs and the procedures for completing and transmitting SAE reports are provided in Recording and Follow-up of AE and/or SAE (Appendix 2, Section 10.2.3 and Section 10.2.4).

Care will be taken not to introduce bias when detecting AEs and/or SAEs. Open-ended and non-leading verbal questioning of the participant is the preferred method to inquire about AE occurrences.

## 8.4.3. Follow-up of AEs and SAEs

After the initial AE/SAE report, the investigator is required to proactively follow each participant at subsequent visits/contacts. All SAEs will be followed until resolution, stabilization, the event

CONFIDENTIAL 51 27 February, 2024

is otherwise explained, or the participant is lost to follow-up (as defined in Section 7.3). Further information on follow-up procedures is provided in Appendix 2, Section 10.2.3.

## **8.4.4.** Regulatory Reporting Requirements for SAEs

- Prompt notification by the investigator to the sponsor of an SAE is essential so that legal obligations and ethical responsibilities towards the safety of participants and the safety of a study intervention under clinical investigation are met.
- The sponsor has a legal responsibility to notify both the local regulatory authority and other regulatory agencies about the safety of a study intervention under clinical investigation. The sponsor will comply with country-specific regulatory requirements relating to safety reporting to the regulatory authority, IRB, and investigator(s).
- An investigator who receives an investigator safety report describing an SAE or other specific safety information (e.g., summary or listing of SAEs) from the sponsor will review and then file it along with the TRP-8802 IB or state other documents and will notify the IRB, if appropriate according to local requirements.
- Investigator safety reports must be prepared for suspected unexpected serious adverse reactions (SUSAR) according to local regulatory requirements and sponsor policy and forwarded to investigators as necessary.
- An investigator who receives an investigator safety report describing an SAE or other specific safety information (e.g., summary or listing of SAEs) from the sponsor will review and then file it along with the IB and will notify the IRB, if appropriate according to local requirements.

# 8.4.5. Pregnancy

- Details of all pregnancies in female participants and in female partners of male participants will be collected for the duration of active intervention.
- If a pregnancy is reported, the investigator will record pregnancy information on the appropriate form and submit it to the sponsor within 24 hours of learning of the female participant or female partner of male participant (after obtaining the necessary signed informed consent from the female partner).
- While pregnancy itself is not considered to be an AE or SAE, any pregnancy complication or elective termination of a pregnancy for medical reasons will be reported as an AE or SAE.
- Abnormal pregnancy outcomes (e.g., spontaneous abortion, fetal death, stillbirth, congenital anomalies, ectopic pregnancy) are considered SAEs and will be reported as such.
- The participant/pregnant female partner of a male participant will be followed until the end of pregnancy, either live birth or termination, to determine the outcome of the pregnancy. The investigator will collect follow-up information on the participant/pregnant female partner and the neonate and the information will be forwarded to the sponsor.
- Any post-study pregnancy-related SAE considered reasonably related to the study intervention by the investigator will be reported to the sponsor as described in Section 8.4.4. While the investigator is not obligated to actively seek this information in former study participants/pregnant female partner, he or she may learn of an SAE through spontaneous reporting.

CONFIDENTIAL 52 27 February, 2024

• Any female participant who becomes pregnant while participating in the study will discontinue study intervention and be withdrawn from the study.

# 8.5. Clinical Safety and Monitoring

At enrollment, potential participants will be appropriately screened for exclusionary psychiatric conditions, medical co-morbidities, and concomitant medications. In addition medical screening will include blood tests including complete blood count (CBC), comprehensive metabolic panel (CMP), urine drug screen (UDS). Subjects with any clinically significant lab abnormalities will be excluded from participation.

Throughout the entire study, suicidal ideation will be assessed during every in-person visit using the C-SSRS and clinical assessment during participant interviews. Significant suicidal ideation is endorsed on items 4 or 5 on the C-SSRS. If the patient screens positive on the C-SSRS at any time during the study, they will undergo a more detailed suicidal risk assessment by study clinician. If they are determined to be at risk of suicide they will be transferred to ED for further Psychiatric evaluation.

During administration, heart rate and BP will be assessed before TRP-8802 capsule administration and at 30, 60, 90, 120, 180, 240, 300, and 360 minutes after capsule administration. Blood pressure and pulse measurements should be preceded by at least 5 minutes of rest for the participant in a quiet setting without distractions (e.g., television, cell phones). If a patient's blood pressure is >200 systolic or >110 diastolic for more than 15 minutes (i.e. 4 consecutive readings) they will be transferred to ED whether or not they are symptomatic.

AEs will be monitored at every study visit. Study staff will also be available throughout the course of the study for emergent AEs. Throughout the administration period, therapists will assess the presence and intensity of participant behaviors, symptoms, and non-verbal cues, which includes questions about the presence/intensity of behaviors, signs, and reported symptoms, such as peacefulness, yawning, nausea/vomiting, quantity of speech, anxiety, sleepiness, crying, restlessness, visual changes, euphoria, and feelings of unreality. They will also complete assessments of mood and safety at the end of the administration sessions.

The session therapists are trained to reassure the participants if they experience acute anxiety, agitation, paranoia, or panic. However, in the unlikely event that those symptoms do not respond to reassurance, or if a participant experiences a severe AE outside of the expected challenging experiences associated with psilocybin therapy, one of the session therapists will contact the on-call study physician. The study physician will use their clinical judgment to determine the most appropriate medical intervention. There will be an automated external defibrillator located on site and a crash cart containing medicine and equipment for emergency resuscitation, including rescue medication as described in section 6.8.1. After dosing sessions, participants will be discharged only if they meet all criteria in section 6.1.2., including being accompanied home by a responsible friend or family member.

During the post-dosing period (visits 6, 7, 9, 10), monitors will also complete assessments of participant mood and safety after therapy visits.

